“Prevention of OUD: The HOME (Housing, Opportunities, Motivation and Engagement) Randomized Trial”

NCT04135703

6/28/2024

Study Protocol

Overview of Design

240 homeless youths between the ages of 18 to 24 years recruited from the streets and drop-in center/shelters will be randomly assigned to 1) 6-months of housing + opioid and related risk prevention services (n = 120), or to 2) opioid and related risk prevention services alone (n = 120). Using an intent to treat design, follow-up assessments will be completed at 3, 6, 9 and 12 months post-baseline. Upon completion of the baseline assessment interview, youths will be randomly assigned to the intervention conditions using a computerized urn randomization program. Four advocates will provide services so that advocate effects can be examined (Baldwin et al., 2011), and each advocate will provide all opioid and related risk prevention services to the youth on their caseload. Advocates will be crossed by condition to “equate” conditions on advocate characteristics.

Sample Inclusion Criteria.

1. Youth were between the ages of 18 to 24 years. Our experience is that landlords will not accept leases signed by youth ages 16-17 years. “Homeless youth” commonly refers to those up to the age of 24 years (Robertson & Toro, 1999; USICH, 2010), thus, this age range generally reflects the age range of the homeless youth population served by providers across the country.
2. Youth met the criteria for homelessness as defined by the federal McKinney-Vento Act (2002) as “lacking a fixed, regular, stable, and adequate nighttime residence” and includes “living in a publicly or privately operated shelter designed to provide temporary living accommodations, or a public or private place not designed for, or ordinarily used as, regular sleeping accommodations for human beings.”
3. Youth failed to meet DSM 5 criteria for Opioid Use Disorder as assessed by the SCID (First et al., 2015).

Screening and intake. Project staff maintain offices within the drop-in center. An RA engaged and screened youth to determine basic eligibility for the study. After the brief screening and stated interest in the project, written consent was obtained and the Structured Clinical Interview for DSM-5 Disorders (SCID) (First, Williams, Karg, & Spitzer, 2015) section on Opioid Use Disorder, was administered to determine formal eligibility.

Project Intervention: Opioid and Related Risk Prevention Services

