Motivational Interviewing (MI). Typically offered as a brief intervention of 1-2 sessions, Motivational Interviewing (MI, Miller & Rollnick, 2012) has a strong record of efficacy in the prevention and treatment of alcohol and other drug use disorders (Copeland et al., 2015; Miller & Rollnick, 2012). MI assumes that the responsibility and capability for change lie within the client and needs to be evoked (rather than created or installed). Baer, Peterson and Wells (2004) provide some rationale for utilizing brief feedback and motivational intervention with street living youth - the intervention is less costly and demands much less of a hard-to-reach population than more intensive interventions. Utilizing a sample of runaway adolescents recruited from a runaway shelter, Slesnick et al. (2013) found that substance use reductions were significant for those assigned to MI even to two years post-treatment. The advocate will administer MI. Four principles guide the practice of MI: express accurate empathy, develop discrepancy, roll with resistance and support self-efficacy. The Project Match manual was adapted for homeless/runaway youth in prior trials in consultation with [name] and [name] (NIAAA grant no. R01AA12173 and NIDA grant R29DA11590). Adaptation of the manual included attention to the unique life situation of homeless youth in understanding motivations and challenges to recovery while homeless. Session 1 begins with a period of open-ended MI, to establish therapeutic rapport and elicit client change talk. In session 2 the advocate continues to focus on enhancing intrinsic motivation for change, developing discrepancy, transitioning as appropriate into the negotiation of a change plan and evoking commitment to the plan.

Housing + Opioid and Related Risk Prevention Services. Those randomized to receive housing + opioid and related risk prevention services will receive all the above and also receive 6-months of rental and utility supports in an apartment of their choosing.

All youth completed a **baseline and follow-up assessment** which included self-report, interview, and physiological measures, with the following outcomes.

Primary Outcomes: **1)** time to OUD (SCID) (UH3) **2)** % days opioid use (Form 90) (UG3, UH3).

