Missing Data. The patterns of missing data will be first examined before each analysis. If data are missing at random, they will be estimated using full information maximum likelihood (FIML) or multiple imputations (MI) method. When data are missing completely at random (MCAR) or are missing at random (MAR), both FIML and ML produce unbiased results (Enders, 2010). The main statistical program used for this study, MPlus, can handle missing data by providing FIML estimation. If the missingness cannot be explained by observed data, that is, data are Missing Not at Random (MNAR), data analysis will be conducted using the pattern mixture model (Roy, 2003) framework.

Study Aim 1. The impact of the two intervention conditions (i.e., 6-months housing + opioid and related risk preventive services, and opioid and related risk preventive services alone) on the primary and secondary outcomes will be tested in Aim 1. Specifically, the primary outcome, time to the onset of OUD, will be analyzed using the discrete-time survival analysis. In this analysis, whether the onset of OUD has occurred at a specific time point is included as the indicator of a latent factor, the proportional odds for the hazard of OUD, which is predicted by the contrasts between conditions. It is expected that youth assigned to the housing + preventive services condition will have longer delay in the onset of OUD than those in the preventive services alone condition. For the primary outcome, % days opioid use, and secondary outcomes that are continuous variables, latent growth models (LGM) will be conducted to estimate the trajectories of change across five time points (baseline, 3, 6, 9 and 12 months follow-up) to estimate the trajectories of change over time. Differences between treatment conditions on estimated growth parameters, including intercepts (i.e., initial status) and slopes (i.e., the rates of change), will be tested. It is expected that those assigned to the 6-month housing + opioid and related risk prevention services group will show greater decreases in opioid use (for those using opioids), as well as greater improvement in secondary outcomes, and that these improvements will maintain for a longer period of time, compared to those assigned to prevention services alone. To increase validity of the conclusions drawn from the analysis, the number of intervention sessions and contacts with other service providers will be covariates in the LGM analyses.

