Statistical Power Analysis. The power analyses were conducted using the Monte Carlo simulation method. The MPI's ongoing study testing the effect of housing support on homeless mothers reveals medium effect sizes in reducing substance use ($d = .49$) and depressive symptoms ($d = .59$), and a large effect ($d = 1.26$) in improving housing stability, favoring the housing intervention over TAU/assessment only. Given that the proposed study tests housing support against an active intervention, and the differences between the two conditions may be smaller than that between housing support and TAU, we assumed small-to-medium effect sizes when conducting the power analysis. For the latent growth analyses, with dichotomous predictors (contrasts between intervention conditions) that have regression coefficients of .15 (small-to-medium effect size) for the slopes of growth factors (Muthén & Muthén, 2002), a sample size of 240, with an overall attrition rate of 15%, can produce a power of .86 to detect the intervention effect on the growth rate of outcomes. For Aim 2, in the simulated mediation analysis, we again assumed a small-to-medium effect size for the intervention effect. Data from the MPI's ongoing clinical trial shows that the associations between social/individual resources and outcomes are of medium effect size or larger (e.g., personal control is associated with depressive symptoms at $r = -.46$ and with general mental health at $r = .43$). Thus we assumed medium effect sizes for the mediator to outcome pathways. Following the model specification suggested by Thoemmes et al., (2010), the proposed sample size could provide a power of .93 to detect mediating effects for the one mediator model and a power of .82 for the serial mediation model with two mediators.

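### If missed visits are left to FIML, OUD first found after a gap inflates the hazard in the arm with more missed-then-recovered visits; the SAP needs a gap-coding rule

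*Combined protocol and SAP*

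**What the plan says.** The Overview of Design states that "follow-up assessments will be completed at 3, 6, 9 and 12 months post-baseline". The inclusion criteria require that "Youth failed to meet DSM 5 criteria for Opioid Use Disorder as assessed by the SCID", so any later OUD is a new onset.

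Under Study Aim 1 the SAP says that "the primary outcome, time to the onset of OUD, will be analyzed using the discrete-time survival analysis", and that "whether the onset of OUD has occurred at a specific time point is included as the indicator of a latent factor". That factor is the proportional odds for the hazard, and condition predicts it.

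The Missing Data section applies one rule to every analysis: "If data are missing at random, they will be estimated using full information maximum likelihood (FIML) or multiple imputations (MI) method". Data judged missing not at random go to a pattern mixture model.

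Attrition appears only under Statistical Power Analysis ("with an overall attrition rate of 15" per cent). It is not split by arm, or into missed visits and permanent loss.

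The documents do not state the period the follow-up SCID covers, how an onset between visits is dated, how OUD first found after a missed visit is coded, or when a youth is censored.

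**The concern.** A youth who misses month 3 and has OUD at month 6 had onset somewhere in months 0 to 6. Applied literally, the generic rule leaves the month-3 indicator missing, its term leaves the likelihood, and the event enters at month 6. The missed interval is gone from the time at risk, but its onset is still counted.

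This is not a failure of the missing-at-random assumption. It happens even when misses are completely random, because the month-6 indicator no longer describes a single interval. The SAP's statement that likelihood methods are unbiased under such missingness therefore gives no protection.

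At stake is a primary comparison in which only one arm gets project-paid housing. Housed youth may be easier to find at each visit. If so, the comparison arm has more gaps, and under this coding the error runs in the hypothesised direction.

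**Working it through.** **The plan's own figure.** None is stated for time to OUD: no incidence, event count or power. The .86 under Statistical Power Analysis concerns the growth model. It cannot be reproduced because the growth variances are not given (assumed values give .57 to .99), and it has no bearing here.

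**Inputs.** From the documents: four follow-up visits, 120 per arm, no OUD at entry, 15% overall attrition. Assumed: no true effect; constant onset hazard h per interval; each visit missed independently with probability m, unrelated to OUD; OUD persists until found; two-sided 5% test.

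**Missed visit left missing, OUD counted when next found (rare onset).**
- Events found at visit k: h(1 − m)(1 + m + … + m^(k−1)) = h(1 − m^k).
- Observed at visit k: 1 − m.
- Hazard inflation at visit k: (1 − m^k)/(1 − m).

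| m | k=1 | k=2 | k=3 | k=4 | mean |
|---|---|---|---|---|---|
| 0.05 | 1.000 | 1.050 | 1.0525 | 1.0526 | 1.0388 |
| 0.10 | 1.000 | 1.100 | 1.110 | 1.111 | 1.0803 |
| 0.20 | 1.000 | 1.200 | 1.240 | 1.248 | 1.1720 |
| 0.25 | 1.000 | 1.250 | 1.3125 | 1.3281 | 1.2227 |

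Null odds ratio, housing against comparison, as the ratio of means:
- 10% against 20% missed: 1.0803/1.1720 = 0.92.
- 5% against 25% missed: 1.0388/1.2227 = 0.85.
- 15% in both arms: 1.00.

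Each pair averages 15% missed. Simulation of the pooled discrete-time model, with 5% to 30% OUD by 12 months, gives the same three values. Rejection at 120 per arm is 4.7–6.9% for the first pair and 6.4–11.2% for the second.

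**Permanent dropout only.** Anyone seen at visit k was seen at every earlier visit, so the inflation is 1 whatever the dropout rate. Simulation gives 1.00–1.01 at every unequal split tried.

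**Mixture.** Take dropout of 5% (comparison) and 2.5% (housing) per interval. Loss by month 12 is 1 − 0.95^4 = 18.5% and 1 − 0.975^4 = 9.6%, about 14% on average. Add intermittent misses of 10% and 5%. The closed form for the gaps alone is 1.0388/1.0803 = 0.96; simulation with the dropout included gives 0.96–0.97.

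**Every missed visit scored as no onset, including those after the last attended visit.** Events over four visits are h[4 − (m + m² + m³ + m⁴)], and exposure is 4. For m = 0.20 the ratio is 3.7504h/4 = 0.9376h; for m = 0.10 it is 3.8889h/4 = 0.9722h. The odds ratio is 0.9722/0.9376 = 1.04, so the direction reverses. Simulation gives 1.04–1.19 with intermittent gaps.

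**Gap kept in the time at risk, censored at the last attended visit.** Events at visit k are h(1 − m^k). Those at risk are youth who attend visit k or later, 1 − m^(5−k). Summed over four visits, both equal 4 − (m + m² + m³ + m⁴) apart from h, so the overall rate is h for any m. Simulation gives a null odds ratio of about 0.99–1.01 at these miss rates.

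**Interval-censored likelihood.** An onset found after a gap contributes 1 − Π(1 − h_t) over the gap and the visit that finds it; for two intervals this is h1 + (1 − h1)h2. Simulation gives 0.99–1.01 in all nine settings tried.

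**The case against.** A reader might infer that the plan dates onset by the visit at which it is found, and so prescribes a biased analysis. The documents do not support that. Study Aim 1 describes an indicator, not a dating rule, and the missing-data sentence is general. A SCID that recovers the onset date would remove the problem, and multiple imputation that uses later visits could limit it. Ordinary event-time coding, with zeros across the gap and censoring at the last attended visit, already gives about 0.99–1.01.

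A reader might also infer that any imbalance in attendance biases the result, or that the error must favour housing. Neither follows. Permanent dropout unrelated to OUD does no harm, and attrition often means exactly that. Scoring missed visits as no onset turns the error against housing. Better attendance by housed youth is plausible but not documented, and both arms receive regular service contact.

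The size is also modest. With 5% onset per interval and 120 per arm, the standard error of the log odds ratio is about 0.32. A null odds ratio of 0.92 is |ln 0.92|/0.32 = 0.083/0.32, or about 0.3 standard errors; 0.85 is 0.163/0.32, or about 0.5.

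All of this stands. What remains is that the plan chooses none of these codings, and that its only written missing-data rule, followed literally, leads to the one that fails.

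**Conclusion.** The concern holds as a conditional one. If missed visits are left as missing indicators and OUD is counted when next found, unequal intermittent gaps distort the hazard comparison even when misses are unrelated to OUD. The null odds ratio is about 0.92 at 20% against 10% missed, about 0.85 at 25% against 5%, and nearer 0.96 if much of the 15% attrition is permanent dropout.

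These sizes rest on assumed attendance by arm, assumed OUD incidence, and OUD persisting until found. If OUD itself lowers attendance by 10 points in both arms, the range under the same coding is 0.86–0.93. The documents do not establish that the trial will use this coding, or which arm will have more gaps. An unwritten choice can move a primary result in either direction, so the rule should be fixed in the SAP.

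**What to change.** State in Study Aim 1 that the survival indicators are not left to FIML across gaps, and add these rules:

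- Code a missed interval as OUD-free when the next attended SCID is negative.
- Treat OUD first found after a gap as interval-censored over the gap, with the likelihood term given above. The simpler alternative is an event at that visit with the gap kept in the time at risk.
- Censor at the last attended visit.
- Report missed-then-recovered visits by arm and visit, separately from permanent dropout.
- Use a recalled onset month only if the SCID already records one.

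The cost is a little extra coding. The interval-censored form needs a purpose-written likelihood; the alternative does not. Both use visit and SCID data that the trial already collects, which matters because parts of the protocol are written in the past tense and a new interview item may come too late. These rules address gaps unrelated to OUD. They do not fully remove bias if attendance depends on OUD: in the 10-point scenario, even exact back-dating of onset gave 1.01–1.03 when attendance was unequal.

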Study Aim 2. To test the proposed behavioral change mechanisms (i.e., social and individual resources), a series of path analysis will be conducted. Specifically, we will first test whether the primary mediator (e.g., service connections, social support) or secondary mediator (e.g., self-efficacy, stress) assessed at the 3- or 6-month follow-up mediates the association between intervention and outcome at 6-month and 9/12-month follow-up, respectively. We expect that the intervention condition with the housing component will produce greater improvement in social/individual resources, which in turn will predict better outcomes. We will also estimate serial mediation models, in which both primary and secondary mediators are included (Figure 1), to test whether intervention first affects social resources, which then lead to changes in individual resources and subsequent outcomes. In these models, the baseline assessment of the mediators and outcomes will be controlled for in the analysis. Following MacKinnon and colleagues (MacKinnon et al., 2007), the product of the coefficient of the path from the independent variable to the mediator(s) and the coefficient of the path from the mediator(s) to the outcomes will be computed as the indirect (mediation) effect between the intervention and outcomes. The strength and significance of the mediation will be estimated using a bootstrap sampling method (Shrout & Bolger, 2002).

Study Aim 3. The effect of the moderating variables (age, sex, race/ethnicity, sexual orientation, childhood abuse history, and baseline substance use and service connection) will be tested by examining the interaction between intervention type and each moderator in predicting outcome slopes in the growth models and survival analysis. The contrast between intervention conditions will be multiplied by each moderator variable to form an interaction term. Next, the interaction terms will be included in the analyses for Aim 1 for the primary/secondary outcomes, one at a time, and their strength of association with the outcome slope will be assessed while controlling the direct effects of the predictors on outcome and the direct effect of moderator variables on outcome. If the interaction term is significant, this suggests moderation.

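### The time-to-OUD model names condition as its only predictor; pre-specifying one baseline opioid-use covariate could recover power, by an amount that the documents do not fix

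*Combined protocol and SAP*

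**What the plan says.** The primary outcomes listed in the study protocol begin with "time to OUD (SCID) (UH3"). In the Statistical Analysis Plan, Study Aim 1, "time to the onset of OUD, will be analyzed using the discrete-time survival analysis", and the latent factor in that model is "the proportional odds for the hazard of OUD, which is predicted by the contrasts between conditions". No further predictor of the hazard is given.

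The one covariate sentence in Aim 1 covers a different model: "the number of intervention sessions and contacts with other service providers will be covariates in the LGM analyses". Those covariates are service counts that accrue after randomization.

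Baseline opioid use is available. Percent days opioid use (Form 90) is the other primary outcome, and its growth model will "estimate the trajectories of change across five time points (baseline, 3, 6, 9 and 12 months follow-up"). It also varies: Aim 1 expects "greater decreases in opioid use (for those using opioids"), and the inclusion criteria exclude OUD at entry but not opioid use.

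Baseline status appears in two other places. In Aim 2 (mediation), "the baseline assessment of the mediators and outcomes will be controlled for in the analysis". In Aim 3, the moderators include "baseline substance use and service connection", tested as interactions with condition, one at a time, in the growth and survival models.

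**The concern.** In a logit hazard model, leaving out a prognostic baseline variable moves the treatment odds ratio toward 1 and lowers the power of the treatment test. Opioid use short of disorder at entry is a natural candidate for such a variable when the endpoint is onset of OUD, and no new data would be needed to use it.

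This matters here because the Statistical Power Analysis covers the growth and mediation models and says nothing about time to OUD. The first-listed primary outcome therefore has no stated power, event count or target effect, and avoidable inefficiency is harder to accept. Naming the covariate in advance also removes a choice that would otherwise be made after the data are seen.

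**Working it through.** **1. The plan's own figure.** There is none for this test. The nearest is .86 for the growth-model slope (coefficient .15, N = 240, 15% attrition). Read as a correlation, two-sided .05, power = Φ(.15·√(n − 3) − 1.96). This gives Φ(2.309 − 1.96) = .64 at n = 240, and Φ(2.127 − 1.96) = .57 at n = 240 × .85 = 204. A five-wave growth model gives about .57 to .96, depending on assumed variances. So .86 is attainable but can be neither confirmed nor refuted, and it does not concern the survival test.

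**2. Scale of the survival test.** Schoenfeld events for 80% power at hazard ratio .5 and 1:1 allocation: 4 × (1.960 + 0.842)² / (ln .5)² = 65.3, so 66. Expected events with control risk p and 15% loss: .85 × 120 × [p + 1 − (1 − p)^.5].
- p = 10%: 15
- p = 20%: 31
- p = 30%: 47

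**3. Effect of adjustment.** Simulated trials had 120 per arm, four follow-up waves, 15% dropout, a logit hazard with four interval intercepts, and a two-sided .05 Wald test of condition; 1,000 trials per cell. N, waves and attrition are from the documents. Alpha, incidence, treatment odds ratio and covariate strength are assumptions. Strength is the log-odds per SD of baseline use: 0.5, 1.0 and 1.5 are odds ratios of about 1.6, 2.7 and 4.5. Entries are power without → with the covariate (continuous).

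| Control OUD, treatment OR | 0 | 0.5 | 1.0 | 1.5 |
|---|---|---|---|---|
| 10%, .5 | .207→.207 | .223→.223 | .195→.209 | .173→.205 |
| 10%, .4 | .320→.316 | .328→.349 | .290→.324 | .259→.322 |
| 20%, .5 | .457→.459 | .462→.471 | .381→.457 | .348→.466 |
| 20%, .4 | .682→.677 | .650→.655 | .593→.660 | .495→.674 |
| 30%, .5 | .651→.644 | .601→.614 | .521→.626 | .434→.607 |
| 30%, .4 | .857→.855 | .796→.827 | .744→.828 | .614→.810 |

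Monte Carlo error is at most √(.25/1000) = 1.6 points per figure. By subtraction:
- Strength 0 to 0.5: −0.7 to 3.1 points.
- 10% incidence: at most 3.4 points up to strength 1.0, and 3.2 to 6.3 at 1.5. A yes/no covariate with 30% users reached 7.7 (.262→.339).
- 20-30% incidence, strength 1.0 to 1.5: 6.7 to 19.6 points.

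At a covariate odds ratio of 2 per SD (1,500 trials per cell), gains were 3 points at 15% incidence (.51→.54, treatment OR .4), 3 at 25% (.53→.56, OR .5) and 5 at 35% (.65→.70, OR .5).

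**4. Attenuation and validity.** At 30%, OR .5, strength 1.0, the mean estimated log-odds was −0.61 unadjusted and −0.70 adjusted (true ln .5 = −0.69). With no treatment effect, rejection rates were .038-.052 unadjusted and .037-.053 adjusted. A further run with yes/no use in 35% gave about .055 adjusted (Monte Carlo error about .006).

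**5. Sparse data.** With yes/no use, 5% incidence and a covariate odds ratio of 10, no non-user had an event in 8-26% of trials; at 10% incidence this fell to 0.5-5%. The covariate's coefficient then has no finite maximum-likelihood estimate.

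**The case against.** Several stronger readings are tempting, and the documents do not support them.

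- **That the primary test is biased or invalid.** It is not: type I error holds without adjustment. Part of the shift in the odds ratio is non-collapsibility, meaning a different estimand. The Aim 1 hypothesis that fewer housed youth will progress to OUD reads most naturally as a marginal statement.
- **That baseline use is the strongest predictor, or that events will be few.** No prevalence, association or OUD rate is given. The text shows only that some enrolled youth use opioids. Both ideas are plausible assumptions, and the gain is close to zero if the association is weak.
- **That imbalance in baseline use goes uncontrolled.** Allocation is by urn randomization, a balancing procedure whose variables are not named. Baseline use may or may not be among them.
- **That the plan contradicts its own Aim 2.** Aim 2 controls the baseline value of each outcome. For OUD that value is constant, because everyone is OUD-free at entry. The growth model for percent days of use already contains its baseline.
- **That covariates are ruled out.** The plan names none; it does not forbid them.

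It is also fair to say that adjustment seldom decides the matter. At a treatment odds ratio of .5, adjusted power in the table never exceeds .65. Only at 30% incidence with odds ratio .4 does it pass .80.

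What remains is that a collected and potentially prognostic baseline variable is not used in the primary model. Aim 3 does not fill the gap: with an interaction in the model, the condition term is no longer the overall treatment effect.

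**Conclusion.** The point holds as a conditional loss of efficiency. The time-to-OUD model has condition as its only named predictor and leaves baseline opioid use unused. Over assumed control incidence of 10-35% and treatment odds ratios of .4-.5, adjustment is worth about 0-4 points of power if baseline use is weakly prognostic or OUD is uncommon, with 6-8 points only in the most extreme 10%-incidence cells. It is worth about 3-20 points if use is strongly prognostic and OUD is common. No single figure should be quoted, because the inputs that determine it are not in the documents. The event count is probably the larger limit on this test, and adjustment would not remove it. This is a worthwhile improvement, between optional and recommended, held with moderate confidence.

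**What to change.** In Study Aim 1, state that the hazard factor is regressed on condition plus one baseline opioid-use covariate, either Form 90 percent days of opioid use or any use (yes/no), and on any variables used for urn balancing. Choose one form now: the two overlap, and with limited events a second adds little. Make this the primary model and report the unadjusted estimate alongside.

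Name a fallback for too few events or separation, for example penalized likelihood or the unadjusted model, with the rule for invoking it. Do not carry the growth model's service-count covariates into the survival model, since they arise after randomization.

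The cost is a few sentences and no new data. The odds ratio becomes conditional on baseline use, a slightly different estimand that the report should state. If outcome data have already been examined, the adjusted analysis must be labelled as specified after that point.
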